During each trial, subjects will ride a stationary bicycle ergometer (Retül Müve, Specialized Bicycle Components Inc., Boulder, CO). Each trial will be 6 minutes long with at least 6 minutes rest between trials. At minutes 4 and 5, we will measure kinematics at 100 Hz, including joint angles, with a 10-camera 3D motion capture system (Vicon, Centennial, CO), kinetics at 1000 Hz, including mechanical power output, with motion capture and force-measuring pedals (Sensix, Poitiers, France) and muscle activity at 1000 Hz using electromyography (Noraxon, Scottsdale, AZ) for approximately 30 seconds. The key muscles that influence bicycling are the vastus lateralis, rectus femoris, biceps femoris, gluteus medius, gluteus maximus, tibialis anterior, soleus, and gastrocnemius [9]; thus we will calculate activation magnitudes and durations for these muscles during each trial, when possible. We will analyze these data with Visual 3D software (C-Motion, Germantown, MD) using a standard anatomical model and a custom software program (Matlab, Mathworks, Natick, MA). We will measure rates of oxygen consumption and carbon dioxide production at standard temperature and pressure dry (STPD) throughout each trial using indirect calorimetry (ParvoMedics TrueOne 2400, Sandy, UT). We will calculate average steady-state metabolic power (W) from minutes 3.5-5.5 of each trial using a standard equation [16]. In our experience, a 6-minute trial duration is sufficient for subjects to reach steady-state metabolic rates. We will adjust trial length as needed if 6 minutes is not sufficient. We will calculate efficiency by dividing the mechanical power (1.5 W/kg) by the average metabolic power in W/kg. We will calculate the degree of mechanical power output symmetry between legs for each configuration

$$SI = \frac{|MechPUL - MechPAL|}{0.5(MechPUL + MechPAL)} \times 100$$

using the symmetry index (SI) as a percentage: where MechP is the mechanical power for the UL and AL of subjects with a TTA. SI values closest to zero are the most symmetric. After each trial, we will ask all subjects to rate their comfort/pain with a Visual Analog Scale (VAS), and subjects with TTAs to rate their comfort/satisfaction with a modified

Prosthesis Evaluation Questionnaire (PEQ). We will use repeated measures analysis of variance (ANOVAs) (significance at $\alpha < 0.05$) with Bonferroni corrections as needed for multiple comparisons to compare data between groups and between legs and determine the optimal PL/PAP/CAL combination (JMPIN, SAS Institute, Cary, NC). We will analyze results from Specific Aim 1 using linear mixed models. We will use a multiple regression and/or principal component analysis to develop optimal prosthetic/bicycle fit guidelines for Veterans with TTAs in Specific Aim 2.

Description of Population to be Enrolled:

We will recruit 15 Veterans with unilateral TTAs who are at or above a K3 Medicare functional classification level (MFCL), and who are 18-55 years old from the VA Jewell Clinic, locally, and nationally. Subjects will give informed consent prior to participation. A K3 MFCL means that a person has the ability or potential for ambulation with variable cadence. A person at K3 MFCL is a typical community ambulator who has the ability to traverse most environmental barriers and may have vocational, therapeutic or exercise activity that demands prosthetic use beyond simple locomotion. Subjects will have no known neurological disease or disorder, and will have no musculoskeletal injuries beyond an amputation. These inclusion/exclusion criteria will minimize any potential confounding variables, thereby increasing the internal validity of the proposed studies. Any person matching the inclusion criteria of the study, regardless of race or gender, will be recruited to participate.

Women and/or minorities will be included in the proposed study. Anyone matching the inclusion criteria of the study, regardless of race, sex, or ethnicity will be recruited to participate.

B. Study Design and Research Methods

Before participants are enrolled in each study, we will complete a pre-screening form and each participant will be asked to give informed written consent. We will ensure that all participants understand the consent form and protocol prior to participation.

Subjects will be asked to complete two experimental sessions at the VA ECHCS/University of Colorado Applied Biomechanics Lab; each session on a separate day at the same time of day, and requiring approximately 2 hours of time. Subjects will be asked to ride a stationary bicycle ergometer (Retül Müve, Specialized Bicycle Components Inc., Boulder, CO) at a fixed power output (1.5 W/kg) and complete a series of experimental trials over two days. On each day, we will measure each subject's height, weight, and limb segment lengths. Then, we will place reflective markers on his/her legs and torso using double-sided tape. These markers will allow us to track his/her body position using our motion capture system. We will also record the forces subjects exert on each pedal using force-measuring pedals. Further, we will measure each subject's leg muscle activity using wireless electrodes that will be placed over his/her muscles using double-sided tape. Finally, we will measure each subject's metabolic rates from the air that he/she breathes out into a mouthpiece. Immediately after each trial, we will ask subjects to rate their satisfaction using a Visual Analog Scale and comfort, fit, effort, etc. with a questionnaire.

On Day 1, we will perform a custom bike fit for each subject according to a protocol developed by Retül for non-amputees (Specialized Bicycle Components Inc., Boulder, CO). Using this protocol, we will systematically vary saddle height and fore-aft position, handlebar vertical and fore-aft position, and alter cleat placement within the shoe for a prosthetic forefoot pedal attachment position, using a conventional crank arm length of 172 mm. Then, we will measure the biomechanics and metabolic rates while subjects ride using the initial fit and three taller pylon lengths for their affected leg in increments of 6.8 mm using a typical pedal attachment position beneath the forefoot. Then, using the optimal (most efficient) pylon length, we will measure the biomechanics and metabolic rates while subjects ride using three shorter crank arm lengths for their affected leg in decrements of 6.8 mm using a typical pedal attachment position beneath the prosthetic forefoot.

On Day 2, we will repeat the protocol of Day 1, but have subjects use a pedal attachment position beneath the pylon for their affected leg. We will randomize the order of days and trials within a day.

D. Description, Risks and Justification of Procedures and Data Collection Tools:

We propose to study healthy people who are familiar with using a prosthesis because this choice minimizes any potential confounding factors associated with novel prosthetic use. Bicycling requires moderate exercise intensity, yet poses no more than minimal cardiac risk for this population. We will restrict our patient age range to comply with the American College of Sports Medicine guidelines. The American College of Sports Medicine (ACSM) Guidelines for Exercise Testing and Prescription (Ninth edition, 2014) classify individuals of any age as having low or moderate risk to participate in an exercise program if they present no more than two of the following risk factors: males age ≥ 45 yrs, females age ≥ 55 yrs, first degree family history of coronary artery disease, cigarette smoking, sedentary lifestyle, obesity, hypertension, dyslipidemia (high cholesterol), and pre-diabetes. These guidelines further recommend that a medical exam and diagnostic exercise testing are not warranted prior to beginning a moderate exercise program for individuals at low to moderate risk. We are being conservative by including patients under 55 years of age (i.e. before their 55th birthday) who do not have any of the other risk factors listed above.

We will comply with Good Clinical Practices (GCPs) by upholding standards for the design, conduct, performance, monitoring, auditing, recording, analysis and reporting of our clinical studies, and by protecting the rights, safety, and well-being of human subjects. We will assure the quality, reliability, and integrity of data collected. We will maintain and monitor GCPs by obtaining Institutional Review Board (IRB)-approval, requiring informed consent, having a data-monitoring plan, reporting Adverse or Serious Adverse Events, having proper documentation, and validating our data collection and reporting procedures.

Foreseeable risks:

1. There is a potential risk of physical discomfort from wearing any type of prosthesis.
2. The adhesive used for motion analysis markers and electrodes may produce slight discomfort.
3. The metabolic analysis mouthpiece and nose clip may produce slight discomfort.
4. Confidential information about participants will be collected as part of this study; therefore, there is a risk of disclosure.

Risk management (corresponds directly to the Foreseeable risks listed above):

1. If you become fatigued, you may ask to rest or stop the study at any time.
2. Before participating in a study, you will be asked if you have any adhesive allergies and if you do, the reflective markers can be placed over tight-fitting clothing.
3. You may ask to remove the mouthpiece and nose clip, rest or stop at any time.
4. Significant efforts will be made to guard against the disclosure of confidential information. All data collected will be de-identified so that your identity is protected; however, the data collected poses no apparent risk to your privacy. We will implement a data and safety-monitoring plan to ensure your privacy. To de-identify your data, you will be given a unique code, and only the research team will have access to the key (linking the code to participant identifiers), which will be kept in a locked cabinet in a locked office. The key will be destroyed upon study completion.

E. Potential Scientific Problems:

Adjustments to PL, PAP, and CAL may not be significantly different from the standard prosthetic/bicycle configuration. In the unlikely event that we find the optimal configuration to be the same as the standard configuration, we will be more confident in the typical recommendations for bicycling and may not need to develop guidelines for optimizing efficiency and comfort. If we find this to be true, we will evaluate how robust this finding is across participants. Within our protocol, we will ask 15 patients with TTAs to complete a VAS and modified PEQ. We predict that use of different PLs, PAPs, and CALs will affect VAS and PEQ scores. We calculated a statistical power of >0.44 to detect a 10% difference in PEQ scores based on 15 participants and the largest standard deviations found in previous studies using the PEQ [23]. Therefore, we may not have adequate statistical power to detect a difference in comfort and fit.

F. Data Analysis Plan:

We predict that different PLs, PAPs, and CALs will affect biomechanics, metabolic costs, and comfort/satisfaction. We calculated effect sizes [17] >0.86 , >0.995 , 0.97 , and >0.44 to detect 10% differences in efficiency (mechanical power/metabolic power), knee and hip joint range of motion, mechanical work output symmetry, and PEQ scores, respectively, based on 15 participants, a repeated measures design, $\alpha=0.05$, and standard deviations found in previous studies [11, 13, 18, 19]. Thus, we feel we have an adequate sample size to detect biomechanical and metabolic differences in our proposed studies, but may not have adequate power to detect differences in PEQ scores.

G. Summarize Knowledge to be Gained:

The proposed research is highly relevant to and will benefit Veterans with transtibial amputations (TTAs). The goal of our research is to challenge the state-of-the-science by developing evidence-based prosthetic and bicycle fit guidelines that optimize the biomechanics, metabolic costs, efficiency and comfort/satisfaction for Veterans with TTAs. Optimizing these parameters through changes in prosthetic and bicycle configurations (i.e. pylon length (PL), pedal attachment position (PAP) beneath the forefoot versus the pylon, and crank arm length (CAL)) will improve rehabilitation and benefit Veterans with TTAs by minimizing injury risk and pain/discomfort, and maximizing physical activity and function; thus facilitating their return to an active healthy lifestyle and/or active duty.

H. References:

1. Ziegler-Graham, K., et al., *Estimating the prevalence of limb loss in the United States: 2005 to 2050*. Arch Phys Med Rehabil, 2008. **89**(3): p. 422-9.
2. US Department of Veterans Affairs, *Fact Sheet. VA Achievements in Diabetes Care, February, 2006*, 2006, <http://www1.va.gov/opa/fact/diabtsfs.asp>.
3. Sambamoorthi, U., et al., *Initial nontraumatic lower-extremity amputations among veterans with diabetes*. Medical Care, 2006. **44**(8): p. 779-787.
4. Ziegler-Graham, K., et al., *Estimating the prevalence of limb loss in the United States: 2005 to 2050*. Archives of Physical Medicine and Rehabilitation, 2008. **89**(3): p. 422-429.
5. Fischer, H., *U.S. Military Casualty Statistics: Operation New Dawn, Operation Iraqi Freedom, and Operation Enduring Freedom*, 2010, <http://www.fas.org/sqp/crs/natsec/RS22452.pdf> Congressional Research Service.

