Specific Aim 1. We will study 15 Veterans with unilateral TTAs to determine the effects of systematically varying PL, PAP beneath the prosthetic forefoot versus the pylon, and CAL for the affected leg (AL) on bicycling biomechanics, metabolic cost, and comfort/satisfaction. **Hypothesis 1.** A taller PL and shorter CAL for the AL compared to the unaffected leg (UL) and a PAP beneath the pylon compared to beneath the forefoot, will maximize mechanical power symmetry and reduce metabolic cost and muscle activity, and thus maximize efficiency and comfort/satisfaction during bicycling in Veterans with unilateral TTAs. Veterans with unilateral TTAs will ride a stationary bicycle ergometer at a fixed power output (1.5 W/kg) and complete a series of experimental trials over 2 days. On Day 1, we will perform a custom bike fit for each subject according to a protocol developed by Retül for non-amputees (Specialized Bicycle Components Inc., Boulder, CO). When fitting riders with TTAs, we will adjust the PL in combination with the socket and prosthetic foot of the AL to match the shank and foot length of the UL. Using this protocol, we will systematically vary saddle height and fore-aft position, handlebar vertical and fore-aft position, and alter cleat placement within the shoe for a forefoot PAP, using a conventional CAL of 172 mm. Then, we will measure the biomechanics (motion, forces, and muscle activity) and metabolic rates while subjects ride using the initial fit and three taller PLs for the AL in increments of 6.8 mm using a PAP beneath the prosthetic forefoot. Then, using the optimal (most efficient) PL, we will measure the biomechanics and metabolic rates while subjects ride using three shorter CALs for the AL in

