decrements of 6.8 mm using a PAP beneath the prosthetic forefoot. On Day 2, we will repeat the protocol of Day 1, but have riders use a PAP beneath the pylon for their AL. We will randomize the order of days and trials within a day. [Because a prosthetic foot cannot flex and extend in a manner similar to the biological ankle, shortening CAL for the AL compared to the UL will reduce the geometric asymmetries between the AL and UL in bicyclists with a TTA. Childers and Kogler estimated that the UL shank and foot have 19.8 mm of displacement throughout the pedal stroke. Moreover, previous studies found differences in biomechanics and metabolic costs during bicycling based on CAL changes of 7.5-15 mm. Thus, we elected to measure the effects of four different CALs within a 19.8 mm range (0 mm, -6.6 mm, -13.2 mm, -19.8 mm) to establish how different prosthetic/bicycle configurations affect biomechanics and metabolic costs across CAL changes. To our knowledge, previous studies have not assessed the effects of changing PL. Thus, we chose to vary PL by the same magnitudes as CAL. We chose to increase PL and decrease CAL because if we lowered PL or increased CAL this would require us to lower the seat height for subjects to reach the bottom pedal position with their AL.

Specific Aim 2. We will synthesize and disseminate our findings from Specific Aim 1 into practical, evidence-based quantitative prosthetic/bicycle fit guidelines for Veterans with TTAs through a multiple regression and principal component analysis. These analyses will take into consideration the body mass, femur lengths, and UL shank and foot dimensions. We will disseminate our guidelines to prosthetists and clinicians in peer-reviewed public-access journals and through conferences/seminars.

II. Background and Significance:

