whether Koutny et al. manipulated CALs for both legs or just changed the CAL for the affected leg (AL). Regardless, reduced muscle activity suggests a lower metabolic cost and thus improved efficiency during bicycling. Childers and Kogler [13] compared the knee and hip joint kinematics and kinetics of 8 cyclists with TTAs with CALs of 172 mm for each leg compared to a CAL of 172 mm for the UL and a CAL of 162 mm for the AL. With asymmetric CALs, knee and hip joint angles and range of motion were more symmetric between legs, but joint kinetics (torque and work) did not change. They suggest that a CAL of 160 mm for the AL would be advantageous for joint angle and range of motion symmetry. However, it is not clear if Childers and Kogler [13] matched the AL height of the pylon and the prosthetic foot to the UL height of the shank and biological foot. Shortening the CAL for the AL could reduce the geometric asymmetry between legs and thus result in more symmetric knee and hip joint angles.] A pilot study (n=3) by Childers et al. [9] found that a 15 mm shorter CAL for the AL versus UL may improve the force symmetry of people with TTAs and thus improve their power output symmetry. They reported that shortening the CAL for the AL versus UL reduced mechanical work asymmetry by 53% [9]. Further, with a shortened CAL on the AL compared to UL, riders reported improved comfort [9]. [Previous studies that varied the anterior-posterior position of the bicycle cleat (PAP) found no effects on metabolic costs for non-amputees, but did find a reduction in gastrocnemius, soleus, and tibialis anterior muscle activations with a forefoot position compared to a heel placement. Childers et al. [9] suggest that the effective prosthetic length, the distance from the knee center to the pedal spindle, should be equivalent between legs in cyclists with unilateral TTAs to minimize kinematic asymmetries. However, no studies to date have determined the optimal PAP or calculated the optimal effective prosthetic length.

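### Minor, free improvement: model the signed symmetry index by rider alongside the absolute one, because the absolute index hides over-correction and can shrink the estimated pylon and crank effects

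*Combined protocol and SAP*

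**What the plan says.** The Outcome Measure(s) section (IV.A) states: "We will calculate the degree of mechanical power output symmetry between legs for each configuration". The index is the absolute difference in mechanical power between the unaffected leg (UL) and affected leg (AL), divided by their mean, times 100. It is read by distance from zero only: "SI values closest to zero are the most symmetric". The sign is therefore dropped before any model is fitted.

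The same section then names repeated measures ANOVA, including comparisons between legs, and adds: "We will analyze results from Specific Aim 1 using linear mixed models". Multiple regression and/or principal component analysis is to produce the Aim 2 fit guidelines. No signed index is described, and no rule for a rider whose AL overtakes the UL.

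Hypothesis 1 under Specific Aim 1 predicts that a taller pylon (PL), a shorter crank arm (CAL) and a pedal position beneath the pylon "will maximize mechanical power symmetry and reduce metabolic cost and muscle activity". The settings move one way only: "three taller PLs for the AL in increments of 6.8 mm", then three shorter CALs starting from the most efficient PL. The CAL rationale gives the levels as "0 mm, -6.6 mm, -13.2 mm, -19.8 mm", that is 6.6 mm steps, while the procedures give 6.8 mm. The two need reconciling, but the difference does not affect this point.

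**The concern.** A rider whose AL gives 45% of the power has a signed index of (55 - 45)/50 x 100 = +20. A rider whose AL gives 55% has -20. The plan records 20 for both. Because the settings all push in one direction, some riders may pass symmetry within a sweep. For them a straight-line response becomes a V, and averaging absolute values near zero adds an upward bias. Two things are at stake: the size of the PL and CAL effects estimated by the mixed models, and the ability of the Aim 2 regression to tell from the index whether a given rider needs more change or less.

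**Working it through.** **The plan's own figures.** Table 1 (Preliminary Studies, one rider) gives signed index values, from (UL - AL)/(0.5 x total) x 100, of 53.0, 47.8, 36.4, 40.0, 31.3 and 27.9%, mean 39.4. This matches the stated split of about 60/40, since (60 - 40)/50 x 100 = 40. The UL dominates in every row. The Data Analysis Plan gives 0.97 for detecting a 10% difference in work symmetry. It cannot be reproduced because no SD is given; with 15 riders and two-sided 0.05, power of 0.97 implies a standardized paired difference of 1.07.

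**Effect size from the documents.** The Background cites a three-rider pilot with a 15 mm change, in which "shortening the CAL for the AL versus UL reduced mechanical work asymmetry by 53" percent. That figure concerns work, not power. Extrapolated linearly:

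- per 6.8 mm step: 53% x 6.8/15 = 24% of baseline, or about 9.6 points from a baseline of 40 (1.413 points per mm);
- over one 20.4 mm sweep: 72% of baseline;
- average asymmetry reaches zero at 15/0.53 = 28.3 mm, beyond one sweep.

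So the mean does not cross zero within a sweep, but individual riders may.

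**Simulation, constant shift.** There are 15 riders and four settings. Per-rider slopes are tested two-sided at 0.05, on signed and on absolute values. The documents give no SDs, so these are assumptions. Set A: rider SD 15, ride SD 8. Set B: rider SD 10 or 15, slope SD 0.5 per mm, ride SD 5. The signed slope was detected in about 100% of trials in every row.

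| Mean baseline | Assumed SDs | Signed slope | Folded slope | Shrinkage | Power, folded |
|---|---|---|---|---|---|
| 40 | A | -7 per step | -6.3 | 10% | 1.00 |
| 40 | B, rider SD 10 | -1.41 per mm | -1.23 | 13% | 1.00 |
| 40 | B, rider SD 15 | -1.41 per mm | -1.11 | 21% | 0.997 |
| 30 | B, rider SD 10 | -1.41 per mm | -0.89 | 37% | 0.98 |
| 30 | B, rider SD 15 | -1.41 per mm | -0.76 | 46% | 0.83 |
| 28 | A | -7 per step | -4.7 | 33% | 0.91 |

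At baseline 40, between 13% (set A) and 23 to 28% (set B) of rides at the last setting fall below zero. The two rows at baseline 30 carry over the shift derived at 40. The cited percentage applied to 30 would give 0.24 x 30 = 7.2 points per step instead of 9.6, so these rows lean toward the larger loss.

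**Simulation, proportional shift.** If each step removes 24% of the rider's own baseline (set A SDs), the folded and signed slopes per step are -4.51 and -4.81 at mean 20, -6.32 and -6.72 at 28, and -9.35 and -9.61 at 40. Folding then costs 3 to 6% of the slope, and power with the folded index is no lower than with the signed one.

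**The case against.** The strongest defence is that Hypothesis 1 concerns maximal symmetry, and for that the absolute index is the right measure: a rise after over-correction is a real loss of symmetry. With mean 20 and -10 per step, mean absolute values over the four settings are 22.0, 15.9, 13.6 and 15.8, and the third setting, where the signed mean is zero, is correctly picked. The plan states no linear trend in the index, and mixed models can treat PL and CAL as categories. This stands, and it is why the absolute index should stay as the Hypothesis 1 outcome.

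A reader might infer that folding loses direction altogether. It does not: power is measured for each leg, and the planned between-legs comparison can show which leg dominates at group level. What is missing is direction per rider in the modelled index.

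A reader might also infer that the effect could vanish or change sign. The documents do not support that. A folded slope of -2.1 with power 0.19 needs mean 20 and -10 per step, which removes 30/20 = 150% of baseline in one sweep against the 72% implied by the cited pilot. A baseline of 20 appears nowhere; Table 1 runs from 27.9 to 53.0. Reversal at baseline 10 with 1.413 points per mm removes 28.8/10 = 288%. Stacking PL and CAL changes, up to 40.8 mm together, could carry riders past zero only if PL acts per mm like CAL, and the Background says PL has not been varied systematically before. The Background also reports eight cyclists whose joint torque and work did not change with a 10 mm shorter crank.

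Last, a signed group mean has its own flaw: riders at +20 and -20 average to zero though neither is symmetric. This also stands and shapes the fix.

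**Conclusion.** The point holds as a minor one. Folding the index for each configuration prevents the models from separating under- from over-correction in an individual rider. If the shift is roughly constant, it also biases the PL and CAL effects toward zero: by about 10 to 20% with almost no power loss near 40% asymmetry, and by about a third to 40% (46% in the widest-spread case) with power about 0.9 (0.83 to 0.98) at 28 to 30%. These sizes rest on assumed SDs, on one pilot rider for the baseline, and on a three-rider estimate for work rather than power. Under a proportional effect the distortion is small. The analysis of Hypothesis 1 is not invalid, and no reversal is shown at the documents' own figures.

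**What to change.** Keep the absolute index as the symmetry outcome for Hypothesis 1. Add the signed index, (MechPUL - MechPAL)/(0.5(MechPUL + MechPAL)) x 100, in a mixed model with rider-level effects. Use it to estimate the PL and CAL effects and as the input to the Aim 2 regression. Define each rider's most symmetric setting as the one whose rider-level predicted signed value is closest to zero. Do not use the group signed mean for this, because riders of opposite sign cancel there. Report both indices side by side.

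The cost is one additional model on data already collected, with no extra rides, measurements or participants. If no rider crosses zero, the two analyses agree apart from sign convention.

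### The plan promises a best combination of pylon length, crank length and pedal position, but the ridden path supports one only if pylon and crank effects do not interact, an assumption that is unstated and untestable within a rider and pedal position

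*Combined protocol and SAP*

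**What the plan says.** The inferential target is in section IV.A (Outcome Measure(s)): repeated measures ANOVA is to compare the data and "determine the optimal PL/PAP/CAL combination". The same section adds linear mixed models for Aim 1, and multiple regression and/or principal components for the Aim 2 fit guidelines. It names no PL x CAL term.

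The rides are set out under Specific Aim 1 and in section IV.B (Study Design and Research Methods):

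- Stage 1: riders "ride using the initial fit and three taller pylon lengths for their affected leg in increments of 6.8 mm", with the bike fitted "using a conventional crank arm length of 172 mm".
- Stage 2: "using the optimal (most efficient) pylon length, we will measure the biomechanics and metabolic rates while subjects ride using three shorter crank arm lengths" for the affected leg.
- The other day repeats both stages with the other PAP.

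Specific Aim 1 explains the levels: "we elected to measure the effects of four different CALs within a 19.8 mm range", and "we chose to vary PL by the same magnitudes as CAL". Nowhere does the plan say that the remaining PL x CAL cells go unridden, or that PL and CAL effects are taken to be additive.

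**The concern.** PL is varied at one crank length only, and CAL at one PL only, which is picked for each rider from that rider's own results. The best CAL at the selected PL is a conditional result. It equals the best pair over the whole grid only if the best PL does not depend on CAL.

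The protocol's reasoning leaves room for such dependence. Specific Aim 1 offers a shorter crank as a way to reduce geometric asymmetry between the legs. Background and Significance suggests a taller pylon because the affected leg has no working ankle. Two adjustments aimed at related geometry may partly replace each other. If they do, PL is tested first and takes the gain, and CAL then shows little at the selected PL.

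At stake is what Aim 2 delivers: named settings in published guidelines. A conditional result could be presented as a joint optimum, and a null CAL result could be read as showing that a shorter crank does nothing at the standard PL.

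**Working it through.** The plan gives no figure for this point. Its power statement (Data Analysis Plan) concerns 10% differences in single outcomes and does not bear on which combination is best.

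**1. Cells ridden.** Four PLs at 172 mm plus three shorter CALs at the selected PL: 4 + 3 = 7 of 4 x 4 = 16 cells per PAP (43.75%). Over two PAPs: 14 of 32.

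**2. Can a rider's data test the assumption?** Code PL as i = 0–3 steps and CAL as j = 0–3 steps, with selected PL o. In stage 1, j = 0, so i x j = 0. In stage 2, i = o, so i x j = o x j. On every ridden cell, therefore, i x j = o x j, an exact multiple of the CAL column. A quadratic surface with one PL x CAL term has rank 5 of 6 for each of the four possible o. The interaction is not estimable within a rider and PAP. The additive model with free levels uses 1 + 3 + 3 = 7 parameters on 7 rides and leaves no residual degrees of freedom.

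**3. Does pooling rescue it?** With k distinct PLs selected across riders, the pooled cells number 4 + 3k. All 16 are covered only at k = 4; k = 2 gives 10. Even then, the interaction is learned by comparing riders sorted by their own outcome. If PL had no effect, about 15/4 = 3.75 riders per PAP would have the initial-fit PL selected.

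**4. How often would the wrong cell be named?** This is illustrative: the surface, the interaction size and the placement of the optimum are all assumed. Cost = u² + v² + 2ρuv, where u and v are the distances in steps from the rider's best PL and CAL. There is no noise, and optima are drawn uniformly over 0 to 3 steps, or over −0.5 to 3.5. Positive ρ means the two adjustments substitute for each other. Gain kept is the total improvement over the standard cell achieved by the path, divided by the total attainable.

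| ρ | Best cell named (0 to 3) | Best cell named (−0.5 to 3.5) | Gain kept (0 to 3) | Gain kept (−0.5 to 3.5) |
|---|---|---|---|---|
| 0 | 100% | 100% | 100% | 100% |
| 0.3 | 58% | 67% | 97% | 97% |
| 0.6 | 38% | 51% | 94% | 95% |
| 0.9 | 31% | 46% | 97% | 98% |
| −0.3 | 58% | 66% | 95% | 96% |
| −0.6 | 39% | 52% | 84% | 88% |
| −0.9 | 31% | 46% | 86% | 91% |

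Averaging each rider's own ratio instead gives 92–97% kept for positive ρ and 69–96% for negative ρ.

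**5. Limiting case.** Suppose cost depends only on the combined change, (i + j − 2)². Stage 1 costs are 4, 1, 0, 1, so PL step 2 is selected. CAL at that PL costs 0, 1, 4, 9: every shorter crank looks worse. CAL at the standard PL would cost 4, 1, 0, 1: the full gain was available from CAL alone.

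**6. Is the full grid feasible?** At 6 minutes per ride and at least 6 minutes of rest, 7 rides take 7 x 6 + 6 x 6 = 78 minutes and 16 rides take 16 x 6 + 15 x 6 = 186 minutes. The session is about 2 hours.

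**The case against.** The procedure is fully disclosed, optimal is defined as most efficient, and nothing says that every combination is ridden. A full grid does not fit the session, so a sequential search is a defensible choice. This stands, and the design itself is not the complaint. It does not rescue the sentence in IV.A, because a disclosed path still supports only a conditional conclusion.

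The simulated percentages depend on an assumed surface and on ignoring noise. That also stands. With an assumed noise SD of one cost unit and optima placed on grid points, even a full grid names the best cell only 52% of the time at ρ = 0.3 and 37% at ρ = 0.9, against 41% and 30% for the path. The estimability result in step 2 needs none of these assumptions.

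Four stronger readings are tempting, and the documents do not support them:

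- *The design can never find the joint optimum.* Without interaction it does target it.
- *The CAL effect at standard PL is never observed.* It is observed in any rider whose most efficient PL is the initial fit, and section IV.E allows that the standard configuration may prove best. What is missing is a planned estimate in all 15 riders.
- *PL and CAL are known to substitute.* No passage says so. The remark "we chose to vary PL by the same magnitudes as CAL" concerns step size, and the limiting case above is a worst case.
- *The CAL part of Hypothesis 1 will be wrongly rejected.* The hypothesis can be read as one joint statement about PL, CAL and PAP. On that reading, testing CAL at the best PL is relevant.

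**Conclusion.** The claim in IV.A is wider than the ridden cells support. The joint optimum is identified in general only under a no-interaction assumption that the plan does not state and cannot test within a rider and PAP. The CAL effect at standard PL comes only from riders selected on the outcome.

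The cell count and the estimability result are exact. The size of the error is not known, because the documents give no information on interaction. Under the assumed noise-free surfaces, the best cell is named about 31–67% of the time at interaction sizes 0.3 to 0.9, with most of the total gain kept: about 94–98% for positive interaction and 84–96% for negative. A reader should not infer a large loss of efficiency. The main risk is that the wrong settings are named, which matters because naming settings is the purpose of Aim 2.

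**What to change.** - In IV.A, replace the stated target with: *determine the best CAL given the most efficient PL, within each PAP*.
- Include the ridden PL in mm in the Aim 1 mixed model, and report CAL effects as conditional on the selected PL. The text gives 6.8 mm steps while the listed CAL offsets step by 6.6 mm, and PL is said to follow the same magnitudes. These passages must be reconciled before the values are coded.
- State the no-interaction assumption wherever a combination is called optimal, including in the Aim 2 guidelines.
- Do not interpret a null CAL result as showing no CAL effect at the standard PL.

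No extra rides are needed. The cost is wording, one model term and a narrower conclusion.
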